Reference therapy	Usual care in the palliative care clinic: stimulant laxative prophylaxis (up to 8 tablets/day of senna or up to 30mg/day of bisacodyl) and/or constipation treatment (osmotic laxative such as polyethylene glycol plus stimulant laxative).
Statistical Methodology	The primary aim of this study is feasibility - specifically, feasibility will be defined as completion of all study drugs over 4 weeks. For the primary aim we believe an acceptable completion rate would be at least 70%. Assuming a true completion rate of 85% (H_A), a sample size of 50 patients would have an 80% power to show that the true rate is at least 70% (H_0), using a one-sided binomial exact test with $\alpha=0.05$. Any dropout after the initiation of study treatment will be categorized as non-completion of study drugs. Thus we plan to recruit until 50 subjects have begun study treatment.

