Treatment of OIC includes both prophylaxis and therapeutic treatment. Since opioids have the unintended consequence of slowing bowel motility, prophylaxis should begin at the initiation of an opioid regimen. Constipation prophylaxis can be approached in a stepwise additive fashion with stimulant laxatives such as senna (1-8 tabs/day) and bisacodyl (maximum 30 mg/day) as the agents of choice. However, patients must titrate these stimulant laxatives based on diet, exercise, fluid intake, and concomitant medication use. Consequently, titrating stimulant laxatives can result in under or overtreatment and be quite burdensome to patients.

Ideally, OIC is prevented, but when it does occur in spite of prophylaxis, it can be effectively treated with the addition of other classes of laxatives (e.g. osmotics, softeners). However, the most specific drug class to specifically reverse OIC is the peripherally acting μ -opioid antagonists. For example, methylnaltrexone (Relistor[®]) is a subcutaneous injection and treatment of OIC in patients with advanced medical illness¹¹ and alvimopan (Entereg[®]) has restricted approval for shortening the course of postoperative ileus.¹² Naloxegol (Movantik[®]), the most recently approved oral, peripherally acting, pegylated derivative of the μ -opioid receptor antagonist naloxone, has been evaluated in non-cancer pain and shown to reduce constipation without reducing opioid-mediated analgesia.¹³ With 25mg of oral naloxegol versus placebo subjects experienced an approximate 15% improvement in response rate (defined as at least 3 spontaneous bowel movements per week and at least one spontaneous bowel movement per week increase over baseline for at least 9 out of the 12 treatment weeks and 3

out of the last 4 treatment weeks during the double-blind treatment period.¹³

Opioid-Induced Constipation Management by UCSD Palliative Care Team

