Secondary objectives will seek to determine the effect of naloxegol versus usual care on OIC, to evaluate naloxegol versus usual care on stool quality (BSS), to describe the adverse events associated with naloxegol when administered daily in this patient population (NCI CTCAE v4.03), to evaluate health related quality of life (PAC-SYM and PAC-QOL), and to evaluate changes in patient reported pain (BPI-sf).

Exploratory objectives will evaluate laxative compliance, healthcare resource utilization, and patient preference to continue naloxegol in the optional 12-week extension period.

Following informed consent, patients will have the following procedures completed to confirm eligibility: physical exam with vital signs, height, and weight, ECOG performance status, complete blood count, comprehensive metabolic panel, and a serum pregnancy test (women of child-bearing potential only). During this screening period, patients will also complete baseline PAC-SYM, PAC-QOL and BPI-sf questionnaires. To confirm OIC, patients will be asked about their frequency of bowel movements in the last week and asked to recall the average BSS that they have experienced. Upon confirmation of all eligibility criteria and within 72 hours of the initial dose of study treatment, patients will be randomized in a 1:1 ratio to either Arm A or Arm B by block randomization. Randomization will be performed by CTRI using a randomization package in the software R (blockrand)^{15,16}. The CTRI office will provide the study coordinator with prestuffed envelopes numbered 1-62. In the envelope, a paper will indicate the treatment assignment. One envelope will be assigned to each patient by the study coordinator in order of accrual. The number on the envelope will become the patient number and will be the identification number on all study documents. Individual patient randomization arm must be assigned prior to the patient being treated on study. The study coordinator will contact IDS once subject randomization arm has been confirmed.

REGIMENT DESCRIPTION				
Treatment Phase	Arm A	Arm B	Schedule	Cycle Length
Initial	Single 25 mg tablet Route: Orally, on an empty stomach 1 hour before breakfast or 2 hours after first meal of the day	Usual Care: stimulant laxative (i.e. up to 8 tablets/day of senna or up to 30mg/day of bisacodyl) ± osmotic laxative (e.g., polyethylene glycol)	Daily, Days 1-14	2 weeks (14 days)

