4.2 Treatment Administration

Patients in Arm A will receive a single daily dose of 25mg naloxegol for the 2-week initial treatment period, followed by a 3-day washout period and 2-week crossover treatment period in which the patient will receive the treating physician's usual care for OIC using a stimulant laxative ± rescue medication.

Patients in Arm B will receive the treating physician's usual care for OIC using a stimulant laxative ± rescue medication for the 2-week initial treatment period, followed by a 3-day washout period and 2-week crossover period in which the patient will receive a single daily dose of 25mg naloxegol.

Patients on Arms A and B will have the option to continue on naloxegol at 25 mg daily for an additional 12-week extension phase upon completion of initial and crossover treatment phases.

Patients will be instructed to take naloxegol on an empty stomach at least 1 hour prior to the first meal of the day or 2 hours after the meal. Tablets must be swallowed whole, and not crushed or chewed by the subject. Subjects will also be instructed to avoid consumption of grapefruit or grapefruit juice as this is a potent inhibitor of the CYP3A4 enzyme.

Patients will also be instructed to complete a daily study drug diary during the treatment phases when naloxegol is being administered. Patients will be asked to bring their completed study drug diary with them during each visit for review with a member of the study team.

If the patient misses their daily morning dose of naloxegol and it has been less than 2 hours since the missed dose, they will be instructed to take naloxegol as soon as it is remembered on the same day. If it has been more than 2 hours since missing a dose, the patient will be instructed to skip the dose for that day not to make up that dose. If the patient vomits after taking a dose, he/she will be instructed not to repeat the dose or attempt to make up that dose.

If a patient takes more than the assigned daily dose of naloxegol, they should be monitored closely for evidence of opioid withdrawal symptoms and reversal of central analgesic effects. In cases of known or suspected overdose, symptomatic treatment as well as monitoring of vital functions should be performed. In cases of severe intoxication, intensive care procedures are recommended. Close medical supervision and monitoring should be continued until the patient recovers.

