Patients may take laxatives during the screening period of the study, but must discontinue use of laxatives at least 3 days prior to Study Day 1. In addition, patients may take an opioid antagonist, mixed antagonist, a strong CYP3A4 and/or P-gp inhibitor, a moderate CYP3A4 and/or P-gp inhibitor, and/or a strong CYP3A4 inducer during the screening period of the study, but must discontinue use of these agents at least 3 days prior to Study Day 1. During the initial and cross over treatment periods, if a bowel movement has not occurred within at least 72 hours, a patient may take bisacodyl as a laxative rescue medication in addition to the dosage of Naloxegol or stimulant laxative. If after a minimum of 72 hours, the patient has not experienced a BM, he/she may take bisacodyl rescue therapy (10-15 mg dose or 2-3 tablets at a time). If the patient remains constipated, bisacodyl rescue therapy may be repeated up to two additional times, as necessary, each 10-15 mg dose separated by 12 hour intervals. It is recommended that the bisacodyl tablets be taken either at bedtime or before breakfast. Of note, both the usual care arm and rescue therapy will use standard doses of bisacodyl (5-15 mg per day). If after 3 doses of rescue therapy, the patient still has not experienced a bowel movement, the investigator may prescribe a one-time use of an enema. The timing of administration of this therapy will be noted on the patient medication use diary. If these secondary interventions fail, the patient should be discontinued from the study and referred for additional medical evaluation. The investigator should recommend initiation of any therapy deemed most appropriate.

Other medication, which is considered necessary for the patient's safety and well-being, may be given at the discretion of the investigator, and will be recorded on the patient medication use diary as well as the concomitant medications case report form.

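### The daily bisacodyl range in Section 4.4 conflicts with the rescue schedule in the same paragraph and with the usual-care ceiling stated elsewhere, and no combined limit is given

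*Combined protocol and SAP*

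**What the plan says.** **Daily range.** Section 4.4 (Permitted Concomitant Therapy) states that "both the usual care arm and rescue therapy will use standard doses of bisacodyl (5-15 mg per day".

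**Rescue schedule.** The same paragraph opens rescue once at least 72 hours have passed without a bowel movement. It describes "bisacodyl rescue therapy (10-15 mg dose or 2-3 tablets at a time", which may be "repeated up to two additional times, as necessary, each 10-15 mg dose separated by 12 hour intervals". Rescue is taken on top of naloxegol or the stimulant laxative. If three doses fail, a single enema may be prescribed; if that fails too, the patient leaves the study.

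**Usual-care ceiling.** The regimen table in Section 4.1 gives usual care as a stimulant laxative, "up to 8 tablets/day of senna or up to 30mg/day of bisacodyl", with or without an osmotic laxative. The Study Summary (Reference therapy) and Section 1.3 give the same bisacodyl ceiling. Section 1.1, on prophylaxis in general, has "bisacodyl (maximum 30 mg/day".

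**Description of usual care in 4.2.** Section 4.2 calls it the treating physician's "usual care for OIC using a stimulant laxative", with or without rescue medication, and does not mention an osmotic laxative.

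**The concern.** The 4.4 sentence is worded as a rule: it says what both usual care and rescue will use, per day. Read that way, it cannot be applied together with the repeat rescue doses described just before it, or with a usual-care ceiling twice as high in three other places. A member of staff who follows one sentence can breach another.

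Three things depend on the reading:

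- **Comparator.** The bisacodyl that may be given as usual care differs. Usual care is the reference for the secondary comparisons in Section 9.3.3 (bowel movements, stool form, PAC-SYM, PAC-QOL, pain).
- **Rescue.** The rescue available in either period differs. Sections 9.3.3 and 9.3.4 mention no adjustment for rescue use.
- **Escalation.** The speed at which a patient moves through three rescue doses to the enema and then to discontinuation differs. Section 9.2 counts dropouts after the start of treatment as non-completers, so this step feeds the primary endpoint.

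**Working it through.** **Inputs**

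| Quantity | Value | Source |
|---|---|---|
| Daily range, usual care and rescue | 5-15 mg | 4.4 |
| Single rescue dose | 10-15 mg (2-3 tablets) | 4.4 |
| Rescue doses allowed | 1 + 2 repeats = 3 | 4.4 |
| Interval | 12 h | 4.4 |
| Usual-care ceiling | 30 mg/day | Study Summary, 1.3, 4.1 |
| Combined limit, usual care plus rescue | none stated | - |

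**Step 1. When does the 5-15 mg range hold?** One rescue dose with no other bisacodyl gives 10-15 mg, which is within the range. That is the only rescue pattern certain to fit. Adding 5 mg of usual-care bisacodyl already gives 15-20 mg.

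**Step 2. Rescue as scheduled.** Place the doses at 0, 12 and 24 h. Any 24-hour window holds at most two doses:

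- at 10 mg: 2 × 10 = 20 mg
- at 15 mg: 2 × 15 = 30 mg

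Both exceed 15 mg. Counting by calendar day does not help: whatever the starting hour, a three-dose course at 12-hour spacing puts two doses, 20-30 mg, into at least one calendar day. The full course is 3 × 10 to 3 × 15 = 30-45 mg, but the third dose falls at 24 h and opens the next window. The like-for-like daily figure is therefore 20-30 mg.

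**Step 3. Usual care alone.** 30 / 15 = 2, a two-fold difference between the ceilings.

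**Step 4. Usual care plus rescue.** Two rescue doses in 24 h add 20-30 mg:

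| Usual-care bisacodyl (mg/day) | With two rescue doses (mg per 24 h) |
|---|---|
| 0 | 20-30 |
| 5 | 25-35 |
| 15 | 35-45 |
| 30 | 50-60 |

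The documents do not say which of these totals is permitted. If rescue counted towards 15 mg, the room left after the smallest rescue dose would be 15 - 10 = 5 mg. A patient taking more than 5 mg of usual-care bisacodyl could then take no rescue, while a patient in the naloxegol period could take one dose.

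**Step 5. Timing of the enema step.** On the 12-hour schedule the third dose comes 24 h after the first, at the earliest 72 + 24 = 96 h after the last bowel movement. If 15 mg per 24 h were binding, only one rescue dose would fit in each 24 h (two make at least 20 mg). Doses would fall at 0, 24 and 48 h, and the third would come at the earliest at 72 + 48 = 120 h. Reading the limit by 24-hour windows is an assumption; the shift under it is 24 h.

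**Step 6. Section 4.1 beside 4.2.** One names an osmotic laxative as the optional addition, the other rescue medication. Both can be true together: usual care as tabulated, plus the rescue open to patients in either period.

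**The case against.** The best defence is that the sentence in 4.4 is an aside, introduced as something to note, and describes a typical amount or an amount per dose. The 30 mg ceiling is stated alike in three places and only this sentence departs from it. Usual care is also meant to be titrated by patient and physician. Bisacodyl is an alternative to senna, so the two-fold gap touches only patients given bisacodyl as usual care, a share the documents do not give. The daily medication diary (Section 5.1.13.2) records rescue laxatives, so actual intake will be known.

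Much of this stands as a limit on the consequences. It does not remove the conflict: the sentence says what both will use per day, and nothing in the protocol marks it as typical or per dose. Flexible care can still carry numeric limits, and those limits must agree. Recording intake shows what was taken, not what was allowed.

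A reader might go further and infer that neither the comparator nor the rescue allowance is fixed. The text does not support that. The rescue drug, the 72-hour trigger, the amount per dose, the three-dose maximum and the one-time enema are stated without conflict, as is the senna ceiling. A reader might also take 4.1 and 4.2 as contradicting each other. But 4.2 does not exclude an osmotic laxative, and polyethylene glycol is not on the prohibited list in 4.5. This is incomplete wording.

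**Conclusion.** The conflict is real and confined to the daily amount of bisacodyl. The range of 5-15 mg per day in Section 4.4 is exceeded by the protocol's own rescue schedule (20-30 mg in 24 h from two doses) and is half the usual-care ceiling given in the Study Summary, 1.3 and 4.1. No combined limit is stated, although rescue is additive. The arithmetic assumes that repeats are taken at the stated 12-hour interval and that the range is a daily total, as written.

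Two further inferences are not supported. Setting the 30-45 mg course total against the daily range compares a course with a day. A claim of harm, or of a bias of given size in the naloxegol versus usual-care contrast, goes beyond the documents: they report no harm at these amounts and give no figures from which a bias could be computed. The sample-size calculation in Section 9.2 uses none of these quantities and is unaffected.

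The point should still be corrected, because these dosing sentences cannot all be followed and they govern the path to discontinuation.

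**What to change.** Reconcile the daily bisacodyl figure in Section 4.4 with the rescue schedule in the same paragraph and with the ceiling in the Study Summary, 1.3 and 4.1. State whether the figure is a limit or a description, whether it applies per dose or per day, and whether rescue counts towards the daily limit in each treatment period. In the same edit, bring the description of usual care in 4.2 into line with the regimen table in 4.1, so that the place of the osmotic laxative is clear. The clinical team must choose the figures; this review takes no view on them.

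The cost is protocol wording, submitted as an amendment under Section 10.8. The endpoints, the sample size and the analysis models stay as they are.

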4.7 Duration of Study Treatment

In the absence of treatment delays due to adverse events, treatment may continue up to a total 16 weeks (treatment periods including optional extension) or until:

- Inter-current illness or worsening of a medical condition that prevents further administration of treatment
- Unacceptable adverse event(s)
- Rescue therapy for patient's constipation fails secondary interventions and/or the investigator believes that other treatment options may be more beneficial
- The investigator believes that study treatment is jeopardizing patient safety
- Patient decides to withdraw from the study, **OR**
- General or specific changes in the patient's condition render the patient unacceptable for further treatment in the judgment of the investigator.

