4.8 Duration of Follow Up

Patients will be followed for occurrence of adverse events for 28 days after removal from treatment or until death, whichever occurs first. Patients removed from treatment for unacceptable adverse events will be followed until resolution or stabilization of the adverse event. Patients will be asked to return to clinic for an end of study visit within 28 days of the final dose of study treatment.

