4.9 Discontinuation from Study Participation

Patients may be removed from study participation at any time or at the discretion of the investigator for any of the following reasons:

- The patient or legal representative withdraws consent to participate;
- The patient is lost to follow-up;
- The patient dies;
- The patient is non-compliant with study procedures;
- The investigator believes that study treatment is jeopardizing patient safety.

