9.0 STATISTICAL CONSIDERATIONS

9.1 Study Design/Study Endpoints

The proposed study is a prospective, single-center, feasibility trial. Ideally, a phase III placebo controlled trial would be completed to demonstrate the efficacy of naloxegol in cancer patients with OIC. However, placebo controlled trials are inherently difficult to accrue to in supportive oncology. Plus, the prior attempt at a phase III placebo controlled trial failed to accrue patients, and was closed early. We believe that a more feasible trial design would be a randomized phase II crossover study. The crossover design has multiple advantages including the potential for increased statistical efficiency requiring smaller sample sizes. Additionally, the crossover study design should appeal to patients more so than a classic placebo-controlled study because all patients will receive the experimental drug that has the potential to offer benefit. Additionally, patients will serve as their own controls, thus minimizing potential confounding factors. A brief washout period before crossover of 3 days based on the elimination half-life of 10 hours (5 half lives, ~50 hours) is also clinically appropriate and is not expected to impact cancer patient symptom management. Prior to embarking on a large phase III placebo controlled crossover study we propose to conduct a smaller simpler phase II crossover study to confirm feasibility of

the crossover strategy.

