9.2 Sample Size and Accrual

The primary aim of this study is feasibility – specifically feasibility will be defined as completion of all study drugs over 4 weeks. For the primary aim we believe an acceptable completion rate would be at least 70%. Assuming a true completion rate of 85% (H_A), a sample size of 50 patients would have an 80% power to show that the true rate is at least 70% (H_0), using a one-sided exact test with $\alpha=0.05$. Any dropout or loss to follow up after the initiation of study treatment will be categorized as a non-completer and remain in the analytic sample. Thus we plan to recruit until 50 subjects have commenced study treatment.

The Palliative Care Service sees approximately 1,200 new inpatient consults and approximately 250 new outpatient cancer consults per year, and is integrated into the cancer care delivery model. OIC is a common symptom in patients with cancer-related pain and requires burdensome self-titration of laxatives for prophylaxis and treatment. Potential study participants will be recruited primarily from the outpatient clinic at Moores Cancer Center, where an estimated 70% of our patient population is currently being treated for OIC. We anticipate that enrollment will be completed in approximately 12 months, therefore, the expected accrual rate is approximately 5 patients per month.

Ethnic Category	Accrual Targets		
	Sex		
	Females	Males	Total
Hispanic or Latino	4	3	7
Not Hispanic or Latino	25	28	53
Ethnic Category: Total of all subjects	29	31	60
Racial Category			
American Indian or Alaskan Native	1	1	2
Asian	3	2	5
Black or African American	4	2	6
Native Hawaiian or other Pacific Islander	1	1	2
White	20	25	45
Racial Category: Total of all subjects	29	31	60

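### Failed rescue ends study participation in section 4.4 but only study treatment in section 4.7, so secondary efficacy data may stop because of the efficacy outcome itself

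*Combined protocol and SAP*

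**What the plan says.** Section 4.4 (Permitted Concomitant Therapy) allows bisacodyl rescue after at least 72 hours without a bowel movement, up to three doses at 12-hour intervals, and then a single enema. It continues: "If these secondary interventions fail, the patient should be discontinued from the study and referred for additional medical evaluation".

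Section 4.7 (Duration of Study Treatment) gives the same event as one of the points at which treatment ends: "fails secondary interventions and/or the investigator believes that other treatment options may be more beneficial".

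Section 4.9 (Discontinuation from Study Participation) opens with "Patients may be removed from study participation at any time or at the discretion of the investigator for any of the following reasons" and gives five reasons: withdrawn consent, loss to follow-up, death, non-compliance, and investigator concern for safety. Failed rescue is not among them.

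Three other provisions bear on what happens to such a patient:

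- **Primary analysis.** Under section 9.2, a dropout after the start of treatment "will be categorized as a non-completer and remain in the analytic sample".
- **Follow-up.** Section 4.8 states: "Patients will be followed for occurrence of adverse events for 28 days after removal from treatment or until death, whichever occurs first". It also states: "Patients will be asked to return to clinic for an end of study visit within 28 days of the final dose of study treatment". Section 5.5 collects PAC-SYM, PAC-QOL and BPI-sf at that visit.
- **Crossover rationale.** Section 9.1 argues that the design will appeal to patients because "all patients will receive the experimental drug that has the potential to offer benefit".

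For the secondary endpoints, section 9.2.1 restricts analysis to patients with baseline and follow-up data and does not define follow-up. Section 9.3.3 gives no rule for failed rescue, a part-observed week or a missing second period.

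**The concern.** Failed rescue is about the clearest failure of the assigned treatment that this trial can record, and it is an extreme value of the bowel-movement endpoint. The site cannot tell from the protocol whether diaries and questionnaires stop at that moment. If staff follow 4.4 as written, observation ends because of the efficacy outcome. Later diary days then come only from patients who did not fail, which flatters whichever treatment has more failures. A failure in the initial period, in either arm, also leaves the patient without a second period, so the within-patient comparison on which the crossover relies is lost for that patient. No count of rescue failures by treatment is planned: section 9.2.1 compares early dropouts with completers on baseline demographics only.

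**Working it through.** **1. The plan's own figure.** Section 9.2 states 80% power with 50 patients, 70% against 85% completion, one-sided exact test at 0.05. The smallest number of completers r with P(X ≥ r | 50, 0.70) ≤ 0.05 is 41. The exact alpha is 0.0402, and power at 0.85 is 0.791. The stated figure is reproduced. Each rescue failure is one of the 50 − 41 = 9 non-completers that the rule tolerates. Nothing in this point disputes the primary calculation.

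**2. How early data can stop.** Take 72 hours without a movement, counted from the start of Day 1. Rescue doses can then fall at 72, 84 and 96 hours, followed by the enema. The earliest failure is about Day 4-5. That precedes the Day 8 PAC-SYM and the Day 18 PAC-QOL, and only part of the first weekly bowel-movement count exists.

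**3. What other provisions recover.** The end-of-study visit in 5.5 collects PAC-SYM, PAC-QOL and BPI-sf, but not the bowel diary or the Bristol Stool Scale. Those two are the efficacy measures named in section 6.3.

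**4. Who misses the second treatment.** With 1:1 allocation and 50 treated, Arm B has about 25 patients. The documents give no failure rate. If 4% to 20% of Arm B failed in the initial period (assumed), 25 × 0.04 = 1 to 25 × 0.20 = 5 patients would never receive naloxegol. This happens under 4.4. It also happens on a plain reading of 4.7, which does not limit the stop to one period.

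**5. Size of the distortion.** All rates here are assumed. Patients who fail have 0.5 movements per week. The others have 3.28 on usual care and 4.10 on naloxegol. Failure occurs in 10% on usual care and 3% on naloxegol.

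Means over everyone:
- Usual care: 0.90 × 3.28 + 0.10 × 0.5 = 3.00
- Naloxegol: 0.97 × 4.10 + 0.03 × 0.5 = 3.99
- Ratio: 3.99 / 3.00 = 1.33

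Two-week means per observed patient-week, with failures contributing week 1 only:
- Usual care: (0.90 × 2 × 3.28 + 0.10 × 0.5) / (1.80 + 0.10) = 5.954 / 1.90 = 3.13
- Naloxegol: (0.97 × 2 × 4.10 + 0.03 × 0.5) / (1.94 + 0.03) = 7.969 / 1.97 = 4.05
- Ratio: 4.05 / 3.13 = 1.29

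The relative benefit falls from 33% to 29%, a loss of about (0.330 − 0.291) / 0.330 = 12% of it.

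**6. Direction.**
- *Equal failure, 10% on both.* Naloxegol over everyone is 0.90 × 4.10 + 0.05 = 3.74, ratio 3.74 / 3.002 = 1.246. Observed, it is (7.38 + 0.05) / 1.90 = 3.91, ratio 3.91 / 3.134 = 1.248. The ratio barely moves, but both means are overstated (3.13 for 3.00 and 3.91 for 3.74).
- *Rates reversed, 3% usual care and 10% naloxegol.* Over everyone, usual care is 0.97 × 3.28 + 0.015 = 3.197 and the ratio is 3.74 / 3.197 = 1.17. Observed, usual care is (6.363 + 0.015) / 1.97 = 3.238 and the ratio is 3.91 / 3.238 = 1.21. The distortion now favours naloxegol.

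**The case against.** The strongest reply is that the sections can be read together. Leaving the study entails stopping treatment, so 4.4 and 4.7 do not strictly exclude each other, and 4.9 is permissive: it omits the event rather than forbidding removal for it. That is fair as logic. It does not tell the site whether to go on collecting diaries, and that is the question that affects the analysis.

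Four stronger readings are tempting, and the documents do not support them.

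- *The worst outcomes leave the data altogether.* They do not. Section 9.2 keeps these patients in the primary analysis, entries made before the failure are already recorded, and 4.8 and 5.5 provide adverse event follow-up and final questionnaires.
- *The mismatch between 4.4 and 4.7 is what keeps Arm B failures from naloxegol.* The loss arises under either section, and only for failures in the initial period. Arm A failures in that period equally miss usual care. The sentence in 9.1 explains the appeal of the design, and any early dropout would run against it in the same way.
- *About a quarter of the relative benefit is lost.* That figure needs the ratio 4.10 / 3.28 = 1.25, in which failures contribute nothing. Section 9.3.3 models both weeks, and data before the failure exist. Only if the undefined follow-up condition in 9.2.1 were read as excluding early failures would 1.25 apply.
- *The bias runs against naloxegol.* No failure rates are given, so its direction is not known.

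It is also fair to say that continued diaries would not show what would have happened on the assigned treatment alone. After failure, the patient receives whatever therapy the investigator recommends.

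**Conclusion.** The point holds for the secondary endpoints. Sections 4.4, 4.7 and 4.9 treat the same event differently and must be reconciled. Under 4.4, collection of the bowel diary, stool scale and in-period questionnaires depends on the efficacy outcome, and neither the end-of-study visit nor 9.3.3 repairs this for bowel movements and stool form. The primary feasibility test is defined and unaffected.

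The size is modest: a two-week ratio of about 1.29 in place of 1.33 under assumed failure rates of 10% and 3%, and next to no change if rates are equal. The illustration assumes that each failure contributes one full week and then nothing. A mixed model may recover part of the difference. With a failure on Day 4-5, even that first week is incomplete. The point is worth correcting because the correction is cheap and because rescue failures by treatment are informative in their own right.

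**What to change.** 1. Reconcile 4.4, 4.7, 4.9 and 9.1, so that one place states whether failed rescue ends the current treatment, all study treatment or study participation, and whether a patient who fails in the initial period may go on to the other treatment. The sponsor decides that rule.
2. Separate ending treatment from ending data collection. Whatever treatment rule is chosen, continue the bowel diary, Bristol Stool Scale, questionnaires and adverse event collection to Day 31 unless consent is withdrawn.
3. Flag all data recorded after treatment stops. State in 9.2.1 that these patients stay in the secondary analyses, and in 9.3.3 how failed rescue, a part-observed week and a missing second period are handled.
4. Report the number of rescue failures by treatment and period. Keep the non-completer rule in 9.2 as it is.

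The cost is protocol wording and extra diaries for a few patients. The drawback is that data after failure reflect whatever therapy the physician gives, so they describe the course after starting the assigned treatment rather than its effect alone and must be interpreted in that way.
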